7.4. Adverse Events (AEs), Serious Adverse Events (SAEs) and Other Safety Reporting

The definitions of AEs or SAEs can be found in Section 9.3.

AEs will be reported by the participant (or, when appropriate, by a caregiver, surrogate, or the participant's legally authorized representative).

The investigator and any qualified designees are responsible for detecting, documenting, and reporting events that meet the definition of an AE or SAE and remain responsible for following up all AEs that are serious, considered related to the study intervention or the study, or that caused the participant to discontinue the study.

The method of recording, evaluating, and assessing causality of AEs and SAEs and the procedures for completing and transmitting SAE reports are provided in Section 9.3.

7.4.1. Time Period and Frequency for Collecting AE and SAE Information

- All AEs and SAEs will be collected from the start of intervention until the follow-up visit at the time points specified in the SoA (Section 1.3 and Section 1.4). However, any SAEs assessed as related to study participation (*e.g.*, study intervention, protocol-mandated procedures, invasive tests, or change in existing therapy) or related to a GSK product will be recorded from the time a participant consents to participate in the study.
- Medical occurrences that begin **before** the start of study intervention but after obtaining informed consent will be recorded as Medical History/Current Medical Conditions **not** as AEs.

- All SAEs will be recorded and reported to the sponsor or designee immediately and under no circumstance should this exceed **24 hours**, as indicated in [Appendix 3](#). The investigator will submit any updated SAE data to the sponsor within **24 hours** of it being available.
- Investigators are not obligated to actively seek information on AEs or SAEs after the conclusion of the study participation. However, if the investigator learns of any SAE, including a death, at any time after a participant has been discharged from the study, and he/she considers the event to be reasonably related to the study intervention or study participation, the investigator must promptly notify the sponsor.

7.4.2. Method of Detecting AEs and SAEs

Care will be taken not to introduce bias when detecting AE and/or SAE. Open-ended and non-leading verbal questioning of the participant is the preferred method to inquire about AE occurrence.

7.4.3. Follow-up of AEs and SAEs

After the initial AE/SAE report, the investigator is required to proactively follow each participant at subsequent visits/contacts. All SAEs, and non-serious AEs of special interest (as defined in Section [7.4.7](#)), will be followed until the event is resolved, stabilized, otherwise explained, or the participant is lost to follow-up (as defined in Section [6.8](#)). Further information on follow-up procedures is given in [Appendix 3](#).

7.4.4. Regulatory Reporting Requirements for SAEs

- Prompt notification by the investigator to the sponsor of an SAE is essential so that legal obligations and ethical responsibilities towards the safety of participants and the safety of a study intervention under clinical investigation are met.
- The sponsor has a legal responsibility to notify both the local regulatory authority and other regulatory agencies about the safety of a study intervention under clinical investigation. The sponsor will comply with country-specific regulatory requirements relating to safety reporting to the regulatory authority, Institutional Review Boards (IRB)/Independent Ethics Committees (IEC), and investigators.
- An investigator who receives an investigator safety report describing an SAE or other specific safety information (*e.g.*, summary or listing of SAEs) from the sponsor will review and then file it along with the Investigator's Brochure and will notify the IRB/IEC, if appropriate according to local requirements.

7.4.5. Pregnancy (Part 1 only)

- Details of all pregnancies in female participants will be collected after the start of study intervention and until follow-up visit (Day 60).
- If a pregnancy is reported, the investigator will record pregnancy information on the appropriate form and submit it to GSK within **24 hours** of learning of the pregnancy in a female participant. While pregnancy itself is not considered to be an AE or SAE,

any pregnancy complication or elective termination of a pregnancy for medical reasons will be reported as an AE or SAE.

- Abnormal pregnancy outcomes (*e.g.*, spontaneous abortion, fetal death, stillbirth, congenital anomalies, ectopic pregnancy) are considered SAEs and will be reported as such.
- The participant will be followed to determine the outcome of the pregnancy. The investigator will collect follow-up information on the participant and the neonate, and the information will be forwarded to the sponsor.
- Any post-study pregnancy-related SAE considered reasonably related to the study intervention by the investigator will be reported to the sponsor as described in Section 7.4.4. While the investigator is not obligated to actively seek this information in former study participants, he or she may learn of an SAE through spontaneous reporting.

7.4.6. Cardiovascular and Death Events

For any cardiovascular events detailed in [Appendix 3](#) and all deaths, whether or not they are considered SAEs, specific Cardiovascular (CV) and Death sections of the eCRF will be required to be completed. These sections include questions regarding cardiovascular (including sudden cardiac death) and non-cardiovascular death.

The CV eCRFs are presented as queries in response to reporting of certain CV MedDRA terms. The CV information should be recorded in the specific cardiovascular section of the eCRF within one week of receipt of a CV Event data query prompting its completion.

The Death eCRF is provided immediately after the occurrence or outcome of death is reported. Initial and follow-up reports regarding death must be completed within one week of when the death is reported.

7.4.7. Adverse Events of Special Interest

The potential risks of otilimab are discussed in Section [2.3](#).

Adverse events of special interest (AESI) include:

- Cytokine release syndrome (CRS) (not related to COVID-19 [see Section [7.4.7.1](#)])
- Serious hypersensitivity reactions
- Infusion site reactions
- Neutropenia \geq Grade 3 ($<1.0 \times 10^9/L$)
- Serious infections

AESIs should be reported as AEs or SAEs, as appropriate. Please refer to Section [9.3](#) ([Appendix 3](#)) and the SRM.

7.4.7.1. Cytokine Release Syndrome

Cytokine-associated toxicity, also known as cytokine release syndrome (CRS), is a non-antigen-specific toxicity that occurs as a result of strong immune activation. The magnitude of immune activation typically required to mediate clinical benefit using modern immunotherapies exceeds levels of immune activation that occurs in more natural settings. As immune-based therapies have become more potent, CRS is becoming increasingly recognized.

Symptomatology associated with CRS and the severity of symptoms varies greatly but may be quite mild, and management can be complicated by inter-current conditions in these participants. This may be particularly the case in patients with severe pulmonary COVID-19 related disease.

Potentially life-threatening severe complications of CRS include cardiac dysfunction, acute respiratory distress syndrome, neurologic toxicity, renal and/or hepatic failure, and disseminated intravascular coagulation. Of particular concern is cardiac dysfunction, which can be rapid onset and severe, but is typically reversible.

In the event of CRS, investigators should follow institutional guidelines for symptom management. Additional guidance can be found in the published literature [Lee, 2014].

For this study, CRS (possibly related to study drug, rather than progression of hyperinflammation in COVID-19 disease) is defined as a worsening of the CRS Grading System (below) **within 6 hours** after start of study drug infusion.

In the event that CRS is suspected (defined as a worsening of the CRS Grading System within 6 hours of drug administration) and is thought to be caused by otilimab by the investigator, additional blood samples should be taken (see Section 1.3 and Section 1.4, and Section 9.2). These blood samples should be taken as soon as possible after suspected CRS onset and then again 24 hours later. The following blood samples should be taken:

- PD (cytokine) sample
- Hematology
- CRP
- D-dimer
- Ferritin

In the event that new onset of CRS is suspected, the medical monitor must be notified immediately and under no circumstance can this exceed **24 hours**, and the event must also be reported within 24 hours as an AE or an SAE. The investigator will submit any updated data related to the CRS event (including completion of any AE or SAE CRF forms) to the sponsor within 24 hours of it being available. Additional CRF forms related to the CRS event should then be completed as soon as possible.

CRS Grading System¹

Grade	Toxicity
CCI - This section contained Clinical Outcome Assessment data collection questionnaires or indices, which are protected by third party copyright laws and therefore have been excluded.	

¹Adapted from Lee, 2014

²Grades **CCI** refer to CTCAE v5.0 grading

7.5. Pharmacokinetics

- Blood samples (approximately 3.5 mL) will be collected for measurement of serum concentrations of otilimab as specified in the SoA (Section 1.3 and Section 1.4).
- The actual date and time (24-hour clock time) of each blood sample collection will be recorded.
- Collection, processing, storage and shipping procedures are provided in the central laboratory manual.
- **Part 2** - If central laboratory kits are not available at a site (for operational reasons), participants can be randomised and dosed, and the PK samples not collected. In this situation, the missing samples would not be a protocol deviation. This is justifiable, because PK sampling is an exploratory endpoint.
- Intervention concentration information that may/would unblind the study will not be reported to investigative sites or blinded personnel until the study has been unblinded.

7.6. Genetics

Genetics are not evaluated in this study.

7.7. Pharmacodynamics

- Blood samples will be collected to help understand the disease, otilimab target levels and response to otilimab in COVID-19 related disease, as specified in the SoA (Section 1.3 and Section 1.4).
- Biomarkers may include, but are not limited to: inflammatory cytokines, such as IL-6; growth factors, such as GM-CSF; and other molecules that are indicative of hyper-inflammation.
- The actual date and time (24-hour clock time) of each blood sample collection will be recorded.
- Collection, processing, storage and shipping procedures are provided in the central laboratory manual.
- **Part 2** - If central laboratory kits are not available at a site (for operational reasons), participants can be randomised and dosed, and the PD samples not collected. In this situation, the missing samples would not be a protocol deviation. This is justifiable, because PD sampling is an exploratory endpoint.

GSK may store samples for up to 15 years after the end of the study to achieve study objectives. Additionally, with participants' consent, samples may be used for further research by GSK or others such as universities or other companies to contribute to the understanding of SARS-CoV-2 infection, associated COVID-19 disease or other diseases, the development of related or new treatments or research methods.

7.8. Immunogenicity Assessments

Antibodies to otilimab will not be assessed as part of this study, since this is a single dose study.

7.9. Health Economics/Medical Resource Utilization and Health Economics

Health Economics/Medical Resource Utilization and Health Economics parameters will not be evaluated in this study.

8. STATISTICAL CONSIDERATIONS

8.1. Statistical Hypotheses

The primary objective of this study is to compare the efficacy of otilimab 90 mg IV versus placebo in participants with severe pulmonary COVID-19 related disease.

In all parts of the study, the study will test the null hypothesis that the difference between otilimab 90 mg and placebo on the proportion of participants alive and free of respiratory failure at Day 28 is less than or equal to zero versus the alternative hypothesis that otilimab 90 mg increases the proportion of participants alive and free of respiratory failure compared with placebo at Day 28.

8.2. Sample Size Determination

Otilimab and placebo will be randomized in a 1:1 ratio.

Part 1

The study will utilize a group sequential design, using a Lan-DeMets alpha-spending function to control the type I error with four interim analyses for futility, two early in the study where futility alone will be assessed, using Pocock analogue rules; and two for efficacy, at later times in the study and at the same time as futility, using the O'Brien-Fleming analogue rules [Lan, 1983]. A sample size of 800 participants will provide approximately 90% power to detect a difference of 12% in the proportion of participants alive and free of respiratory failure at a one-sided 2.5% significance level and an assumed placebo response rate of 45%. The minimal detectable effect for this design is 7%.

Full details of the decision criteria and interim analysis plan will be given in the IDMC charter and analysis plan.

The assumed placebo response is based on data from recent publications of studies of patients with severe pulmonary COVID-19 related disease [Sanofi, 2020].

Part 2

A sample size of 346 participants will provide approximately 80% power to detect a difference of 15% in the proportion of participants alive and free of respiratory failure at a one-sided 2.5% significance level and an assumed placebo response rate of 45%. The minimal detectable effect for this design is 10.6%.

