5.2.2.1. Decision Criteria

Guidelines for stopping the study for futility (*e.g.* lack of efficacy) or overall success (*e.g.* evidence of efficacy) based on the primary endpoint are detailed below.

Futility will formally be assessed 28 days after approximately 160 participants have been randomised and will then be assessed 28 days after approximately 280, 400 and 600 participants have been randomised. Study success will be assessed 28 days after approximately 400 and 600 participants have been randomised.

Study stopping criteria have been defined using group sequential design methodology, using a Lan-DeMets alpha-spending function to control the type I error to 2.5% one-

sided, with four interim analyses for futility, using Pocock analogue rules with a beta-spend of 10%; and two for efficacy, using the O'Brien-Fleming analogue rules [Lan, 1983].

Table 5 gives the stopping boundaries based on p-values (one-sided) from the analysis and also on the Z score scale. The p-values or Z scores at each interim analysis will be plotted against the boundaries and if either the futility or efficacy success boundary is crossed the study should be recommended to stop.

The boundaries are based on the estimated amount of information at each interim. If the amount included in interim analyses 1-4 differs from these values, the actual boundaries will be determined based on the exact amount of information at the time of the interim analyses. Note: The boundary at interim 5 is based on the estimated amount of information per the planned sample size of N=800, it will not be updated based on the actual sample size.

Table 5 Formal Stopping Boundaries for Futility and Efficacy Success

Stage / Formal Analysis	Target Sample Size	Efficacy Success Boundaries		Futility Boundaries	
		p-value	Z-Score	p-value	Z-Score
1	160			>0.6005	<-0.2548
2	280			>0.3938	<0.2693
3	400	<0.0015	>2.9626	>0.2308	<0.7363
4	600	<0.0092	>2.3590	>0.0744	<1.4441
5 – Final Analysis	800	<0.0220	>2.0141	>0.0220	<2.0141

As recruitment has completed prior to formal interim analysis number 4 (on approximately 600 participants), it was decided to remove this formal pre-specified analysis on approximately 600 participants and continue to the final analyses only. The final analysis boundary has been adjusted to carry over the alpha that would have been spent on the 600-participant analysis as per Table 6. Previous boundaries were not amended.

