Table 6 Final Analysis Stopping Boundaries for Futility and Efficacy Success

Stage / Formal Analysis	Target Sample Size	Efficacy Success Boundaries		Futility Boundaries	
		p-value	Z-Score	p-value	Z-Score
Final Analysis	800	<0.0244	>1.9697	>0.0244	<1.9697

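### Part 1's stated 90% power for a 12-point difference falls to about 86% (original boundaries) or 87% (current design) when the plan's own futility boundaries are followed

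*Protocol*

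**What the plan says.** Protocol 8.2 sets out a Part 1 group sequential design with four futility looks, two of which also test efficacy, and then gives the power: "A sample size of 800 participants will provide approximately 90% power to detect a difference of 12" percentage points, "at a one-sided 2.5% significance level and an assumed placebo response rate of 45"%. Allocation is equal ("Otilimab and placebo will be randomized in a 1:1 ratio"). Part 1 SAP section 3 gives the same power statement.

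Part 1 SAP 5.2.2.1 describes the stopping rules as a design "with four interim analyses for futility, using Pocock analogue rules with a beta-spend of 10"%, and says that "if either the futility or efficacy success boundary is crossed the study should be recommended to stop". Table 5 prints the boundaries for analyses at 160, 280, 400, 600 and 800 participants.

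The same section then removes the 600-participant look because recruitment had already finished: "The final analysis boundary has been adjusted to carry over the alpha that would have been spent on the 600-participant analysis". Table 6 ("Final Analysis Stopping Boundaries for Futility and Efficacy Success") moves the final Z boundary from 2.0141 to 1.9697, and the earlier boundaries stand. The power sentence in section 3 was not changed.

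**The concern.** A 10% beta-spend means that the total probability of failing at the design alternative, with futility stops counted, is 10%. It should therefore match the 90% power in the sample-size section. That match holds only if the boundaries were calibrated to the effect that 800 participants are said to detect. A fixed design needs only 719–726 participants in total for 90% power here, so 800 carries a margin for the interim looks. The question is whether that margin covers four Pocock-type futility looks, which spend beta early.

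If it does not, readers of the protocol, the SAP and the study report take the risk of missing a 12-point benefit to be 10% when it is larger. The point is about a pre-trial design property. It says nothing about Part 1's result or the reasons for Part 2.

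**Working it through.** **Inputs**

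- Protocol 8.2: N = 800, 1:1 (400 per arm), one-sided 2.5%, placebo 45%, difference 12 points, so 45% versus 57%.
- Part 1 SAP Tables 5 and 6, Z scale:

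| Analysis (n) | Information fraction | Futility Z below | Efficacy Z above |
|---|---|---|---|
| 160 | 0.20 | −0.2548 | none |
| 280 | 0.35 | 0.2693 | none |
| 400 | 0.50 | 0.7363 | 2.9626 |
| 600 (Table 5 only) | 0.75 | 1.4441 | 2.3590 |
| 800, Table 5 | 1.00 | 2.0141 | 2.0141 |
| 800, Table 6 | 1.00 | 1.9697 | 1.9697 |

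**Step 1. Find where the boundaries give the plan's 90%.** The Pocock-type spend is 0.1 × ln(1 + (e − 1)t). At t = 0.20, 0.35, 0.50, 0.75 and 1 it equals 0.0295, 0.0471, 0.0620, 0.0828 and 0.1000. Recursive integration of the joint normal distribution of the interim Z statistics, using the Table 5 boundaries, gives exactly these cumulative futility probabilities when the expected final Z (the drift) is 3.651. Power there is 90.0%. The first look can be checked by hand: Φ(−0.2548 − 3.651 × √0.2) = Φ(−1.888) = 0.0295. The boundaries were therefore built to give 90% with futility included, at a drift of 3.651.

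**Step 2. Find the drift that 12 points and 400 per arm supply.**

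- Pooled variance: 0.12 / √(2 × 0.51 × 0.49 / 400) = 0.12 / 0.03535 = 3.395
- Unpooled variance: 0.12 / √((0.45 × 0.55 + 0.57 × 0.43) / 400) = 0.12 / 0.03509 = 3.420
- Log odds ratio: 0.4825 / √((1/0.2475 + 1/0.2451) / 400) = 0.4825 / 0.1425 = 3.387

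All three fall short of 3.651. The first look already shows the effect: with pooled variance, Φ(−0.2548 − 3.395 × √0.2) = Φ(−1.773) = 0.0381, against a planned spend of 0.0295.

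**Step 3. Calculate power at 12 points by recursive integration.**

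| | Log odds | Pooled | Unpooled |
|---|---|---|---|
| Table 5, futility followed | 85.6% | 85.7% | 86.2% |
| Table 6, futility followed | 87.0% | 87.1% | 87.5% |
| Table 5, futility ignored | 91.9% | 92.0% | 92.4% |
| Table 6, futility ignored | 92.2% | 92.3% | 92.7% |

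A binomial simulation with one million trials per case gives 85.8% (Table 5) and 87.3% (Table 6) with futility followed. For comparison, a fixed design with 400 per arm and no looks has 92.6% power.

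**Step 4. Find what 90% would need.** The drift for 90% is 3.651 under Table 5 and 3.576 under Table 6.

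- Difference at N = 800: 12.8–12.9 points (Table 5) or 12.5–12.7 points (Table 6).
- N at 12 points with the same information fractions, 800 × (required drift / drift at 12 points)²: for Table 5, 800 × (3.651/3.4195)² = 912 to 800 × (3.651/3.3866)² = 930. For Table 6, 875 to 892.

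**Step 5. Check type I error.** With futility ignored, one-sided alpha is 0.0250 (Table 5) and 0.0249 (Table 6). It is controlled whether or not futility is followed.

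**The case against.** The strongest defence is that futility is advisory. SAP 5.2.2.1 introduces the boundaries as guidelines, a crossing leads only to a recommendation, and the full stopping details are in the IDMC charter, which is not part of these documents. The efficacy boundaries control alpha without credit for futility, so the trial could continue past a crossing. On that reading power is about 92–93% and the stated figure is met. It is true that the two readings lie either side of 90% and that protocol 8.2 does not say which it uses. But a futility boundary that is non-binding for alpha still costs power whenever it is acted on. The SAP states a 10% beta-spend and a recommendation to stop, and the boundaries reproduce that spend at every analysis only when futility stops are counted. Nothing in the documents says the 90% leaves them out.

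Four smaller points limit the finding without removing it.

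- The word approximately gives some latitude, and the current-design shortfall is 2.5–3.0 points. Even so, a 10% miss probability becomes 12.5–13.0%.
- The 86% figure describes a design that has been superseded, although protocol 8.2 still describes that design.
- Interim boundaries were to be recalculated if the information differed from plan, so these figures apply to the planned fractions.
- The primary analysis adjusts for baseline clinical status and age group, which may add power. Closing the gap at 12 points would take about 9–12% more information under Table 6 (875/800 to 892/800) or 14–16% under Table 5 (912/800 to 930/800). The documents give no figure for the covariates' prognostic strength.

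**Conclusion.** The concern holds. With the printed boundaries followed at the planned information fractions, Part 1's power for 45% versus 57% is 85.6–86.2% under Table 5 and 87.0–87.5% under Table 6, against a stated figure of about 90%. The probability of missing a 12-point difference is 13.8–14.4% or 12.5–13.0%, not 10%. The ranges cover the log-odds, pooled and unpooled variance forms, and none of them reaches 90%. The sample-size sentence and the boundary table were set for different effects: 12 points in one and about 12.8–12.9 in the other.

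The conclusion rests on futility crossings leading to a stop, and on an unadjusted analysis with complete outcome data. Type I error is intact. Part 1 had already enrolled 806 participants by Amendment 3, so this concerns the accuracy of a headline design figure and not the conduct of the trial. Part 2 has no futility or efficacy look and is not affected.

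**What to change.** Restate the power sentence in protocol 8.2, Part 1 SAP section 3 and the study report, along these lines:

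> With the futility boundaries followed, 800 participants give about 86% power for a 12-point difference under the original boundaries (90% at about 12.9 points), and about 87% after removal of the 600-participant look (90% at about 12.6 points). If futility is treated as non-binding, power is about 92%. These are pre-trial figures, unadjusted for covariates.

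The cost is one sentence and a slightly less favourable power figure. Enrolment, boundaries and analyses do not change.
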